4.1.8 Handling of Missing Data for the Secondary Endpoint of Fever resolution

Three days of non-fever are required for the confirmation of fever resolution. If after a non-fever is observed and the next 2 days are missing in the e-diary, then fever status (not the same day temperature) on the first non-missing will be used in the confirmation. That is, resolution of fever requires 3 sequential days of non-fever recorded in the e-diary, which may not be consecutive days, if there is missing data.

4.2 ANALYSES OF SECONDARY EFFICACY ENDPOINTS

4.2.1 Survival/Mortality

The overall survival rate (the proportion of randomized subjects who survive up to Day 15 and Day 28) will be summarized using the same approach as the primary outcome.

4.2.2 Clinical Improvement

Time to resolution of fever from randomization up to Day 28 will be analyzed with Kaplan Meier⁵ survival analyses. A log-rank test will be used to compare this time-to-event outcome between groups. The median event time and their corresponding 2-sided 95% CIs will be provided for each treatment arm. The analysis will treat subjects who die and have not yet had a fever resolve as having their fever having not been resolved at Day 28. A sensitivity analysis of this analytical approach will be performed, and the interpretation discussed in the Clinical Study Report.

Time to COVID-19 related Hospitalization/ER visit or Death (disease progression) will be provided using a similar approach as to time to fever resolution.

If needed, between group comparisons will be made accounting for covariates that may be associated with outcome which clinically significant baseline differences were observed despite randomization as determined by the Sponsor Safety Monitor and Principal Investigator using a proportional hazard (Cox) regression⁶.

Proportion of subjects with no viral shedding (yes/no) using RT-PCR at Day 7, Day 15, and at early termination will be analyzed using the approach specified for the primary endpoint.

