8.3 COVID-19 RT-PCR Test at Central Laboratory

Subjects who test positive for COVID-19 at the local laboratory will be enrolled if the subject meets all other entry criteria requirements. Nasal mid-turbinate swab samples are also to be obtained at the Screening/Baseline and Day 1 visit for central laboratory viral testing for COVID-19 as a baseline assessment and to test for viral shedding. If a subjects' test performed at the local laboratory is positive for COVID-19 but the test performed at the central laboratory is negative, the subject will stay in the study and complete all study visits. The reason for this is that RT-PCR testing is not sensitive enough to be accurate 100% of the time. These subjects will provide safety data for camostat mesilate. Statistical analysis for efficacy endpoints may be adjusted for subjects who fall into this category.

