13.3.2 Analysis of Secondary Efficacy Endpoints

Secondary analysis include:

- The overall survival rate (the proportion of randomized subjects who survive up to Day 15 and Day 28)
- Time to resolution of fever from randomization up to Day 28
- Time to hospitalization or death following randomization up to Day 28

- Proportion of subjects with no viral shedding (yes/no) using RT-PCR at Day 7 and Day 15

The overall survival rate up to Day 15 and Day 28 will be analyzed in ITT and PP populations similar to the primary analysis.

Similar methods, as per the primary endpoint, will be used to analyze the proportion of subjects with no viral shedding at Day 7 and Day 15. Time to resolution of fever from randomization up to Day 28 and time to hospitalization or death will be summarized with Kaplan-Meier curves. A log-rank test will be used to analyze those time-to-event endpoints. The median event time and their corresponding 2-sided 95% CIs will be provided for each treatment arm. The Cox proportional hazard model with treatment group, sex, race, duration of symptoms prior to enrollment, age groups (< 65 versus \geq 65 years) and other risk factors as covariates may be used to investigate the potential influences of demographic and baseline characteristics. The hazard ratios and their 95% CIs will be estimated. Additionally, the change from baseline in clinical symptoms and viral shedding will be summarized using shift tables.

A sensitivity analysis for the secondary efficacy endpoints will also be performed for central laboratory confirmed COVID-19 subjects in the ITT population.

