2.5 ANALYSIS SETS

2.5.1 Intent-to-Treat Population (ITT)

The Intent-to-Treat (ITT) population will include all subjects who are randomized. Subjects will be analyzed according to their study treatment assignment, not according to the treatment actually received. The ITT population is the primary population and will be used for evaluating primary and secondary efficacy endpoints and subject baseline characteristics.

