Table 14.2.2.1 – Counts and Percentages Surviving to Days 15 and 28 Days by Treatment Group in ITT	Table 14.2.2.1	ITT
Table 14.2.2.2 – Counts and Percentages Surviving to Days 15 and 28 Days by Treatment Group in PP1	Table 14.2.2.2	PP1
Table 14.2.2.3 – Counts and Percentages Surviving to Days 15 and 28 Days by Treatment Group in PP2	Table 14.2.2.3	PP2
Table 14.2.3.1 – Time to Resolution of Fever by Treatment in ITT Analysis Set	Table 14.2.3.1	ITT
Table 14.2.3.2 – Time to Resolution of Fever by Treatment in PP1 Analysis Set	Table 14.2.3.2	PP1
Table 14.2.3.3 – Time to Resolution of Fever by Treatment in PP2 Analysis Set	Table 14.2.3.3	PP2
Figure 14.2.4.1 – Kaplan-Meier Time to Resolution of Fever in ITT	Figure 14.2.4.1	ITT
Figure 14.2.4.2 – Kaplan-Meier Time to Resolution of Fever in PP1	Figure 14.2.4.2	PP1
Figure 14.2.4.3 – Kaplan-Meier Time to Resolution of Fever in PP2	Figure 14.2.4.3	PP2
Table 14.2.5.1 – Time to COVID-19 Hospitalization/ER visit or Death by Treatment in ITT	Table 14.2.5.1	ITT
Table 14.2.5.2 – Time to COVID-19 Hospitalization/ER visit or Death by Treatment in PP1	Table 14.2.5.2	PP1

TLF Name	TLF Number	Population
Table 14.2.5.3 – Time to COVID-19 Hospitalization/ER visit or Death by Treatment in PP2	Table 14.2.5.3	PP2
Figure 14.2.6.1 – Kaplan-Meier Time to COVID-19 Hospitalization/ER visit by Treatment in ITT	Figure 14.2.6.1	ITT
Figure 14.2.6.2 – Kaplan-Meier Time to COVID-19 Hospitalization/ER visit by Treatment in PP1	Figure 14.2.6.2	PP1
Figure 14.2.6.3 – Kaplan-Meier Time to COVID-19 Hospitalization/ER visit by Treatment in PP2	Figure 14.2.6.3	PP2
Table 14.2.7.1 – Proportion of Subjects with No Viral Shedding at Days 7, 15, and at Early Termination in ITT	Table 14.2.7.1	ITT
Table 14.2.7.2 – Proportion of Subjects with No Viral Shedding at Days 7, 15, and at Early Termination in PP1	Table 14.2.7.2	PP1
Table 14.2.7.3 – Proportion of Subjects with No Viral Shedding at Days 7, 15, and at Early Termination in PP2	Table 14.2.7.3	PP2
Table 14.2.8.1 – Shift Table of Fever Severity Categories	Table 14.2.8.1	ITT
Table 14.2.8.2 – Shift Table of Fever Severity Categories	Table 14.2.8.2	PP1
Table 14.2.8.3 – Shift Table of Fever Severity Categories	Table 14.2.8.3	PP2
Tables Safety		
Table 14.3.1.1 - Overall Summary of Adverse Events by Treatment	Table 14.3.1.1	SP
Table 14.3.1.2 – Adverse Events Occurring in 5% of Subjects in Either Treatment Group by MedDRA System Organ Class and Preferred Term	Table 14.3.1.2	SP

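### The SAP leaves out the protocol's central-laboratory-confirmed sensitivity analyses and its viral-shedding shift table; the gap matters most for viral shedding, where subjects negative at baseline dilute the ITT comparison.

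*SAP*

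**What the plan says.** **Entry and retention.** Protocol 8.1 bases entry on a positive local test. A swab for the central laboratory is taken at the Screening/Baseline and Day 1 visit, but its result does not decide eligibility. Under Protocol 8.3, if the local test is positive and the central test negative, "the subject will stay in the study and complete all study visits". The same section allows that efficacy analyses may be adjusted for such subjects.

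**Protocol analyses.** Protocol 13.3.1 says that a sensitivity analysis in central-laboratory-confirmed subjects will be done for the primary endpoint. Protocol 13.3.2 extends it: "A sensitivity analysis for the secondary efficacy endpoints will also be performed for central laboratory confirmed COVID-19 subjects in the ITT population". Protocol 13.3.2 also plans shift tables for the change from baseline in viral shedding.

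**SAP analyses.** SAP 2.5.1: "The Intent-to-Treat (ITT) population will include all subjects who are randomized". That set is primary and "will be used for evaluating primary and secondary efficacy endpoints and subject baseline characteristics". SAP 3.2 classifies each subject as shedding or not, without reference to baseline. SAP 4.2.2 assigns the method: "Proportion of subjects with no viral shedding (yes/no) using RT-PCR at Day 7, Day 15, and at early termination will be analyzed using" the primary-endpoint approach. The ITT table in the SAP appendix is "Table 14.2.7.1 – Proportion of Subjects with No Viral Shedding at Days 7, 15, and at Early Termination in ITT", with repeats in PP1 and PP2 only.

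**Precedence.** SAP section 1 says that the SAP prevails where it differs from the protocol, and describes the SAP as a stand-alone document for the essential statistical approaches.

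**The concern.** An analysis that the protocol commits to, for the primary endpoint as well as the secondary ones, has no counterpart in the document that governs the analysis. If it is run only after unblinding, it will look like a post hoc choice.

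The omission matters most for viral shedding. A subject who is negative on the central swab before the first dose and negative again at Day 7 counts as not shedding, although no clearance was observed. Such subjects add about the same number of favourable results per head to both arms and pull the ITT difference toward zero. This is the only virological endpoint, and it bears directly on the viral-entry mechanism described in Protocol 7.2. SAP 4.1.6 says that the totality of evidence will inform the Phase III decision, so a diluted virological result without its planned companion analysis could mislead that decision.

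**Working it through.** **1. Is the analysis anywhere in the SAP?**

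| Place in SAP | What it contains | Central baseline RT-PCR used? |
|---|---|---|
| 2.5 Analysis sets | ITT, PP1 (80% compliance), PP2 (no major deviations or confounding intercurrent events), Safety | No |
| 4.1.1 to 4.1.6 Primary methods | Unadjusted test, subgroup display, covariate models | No |
| 4.1.7 Missing data | Imputation model with age, BMI, sex, symptom duration, clinic temperatures | No |
| 4.2 Secondary methods | Primary approach or Kaplan-Meier/log-rank | No |
| 4.4 Subgroups | Ten classifications | No |
| 4.7 Protocol deviations | A negative central test is not listed, so PP2 does not clearly remove these subjects | No |
| 5 Table list | Viral shedding in ITT, PP1, PP2; shift tables for fever severity and laboratory values only | No |

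**2. Check of the power calculation.** The documents give no rate, power or sample size for viral shedding. The nearest stated figure is 80% power for the primary endpoint (15% vs 30%). Exact enumeration gives 80.2% for Fisher's test at the protocol's 183/92, which reproduces it. At the SAP's 186/93, exact power is 83.0% for the unadjusted Pearson test, 80.2% for Fisher and 78.9% with continuity correction.

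**3. Dilution formula.** Let q be the share central-negative at baseline, s the probability that such a subject is negative at the visit (same in both arms), and p the clearance rate in baseline positives.

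- Observed rate in an arm = (1 − q)·p + q·s
- The q·s term cancels between arms, so ITT difference = (1 − q)·(p_active − p_placebo)

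With no drug effect, p is equal in the arms and the ITT difference is zero for any q. Type I error is therefore not affected.

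For a 15-point difference:

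- q = 5%: 0.95 × 15 = 14.3 points
- q = 10%: 0.90 × 15 = 13.5
- q = 20%: 0.80 × 15 = 12.0
- q = 30%: 0.70 × 15 = 10.5

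Example at q = 10%, s = 95%, 30% vs 45%: placebo 0.9 × 0.30 + 0.1 × 0.95 = 36.5%; active 0.9 × 0.45 + 0.1 × 0.95 = 50.0%; difference 13.5 points.

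**4. Power.** Assumptions: s = 95%; 186/93 subjects in all; the baseline-positive set is 186(1 − q)/93(1 − q), rounded; two-sided 5% Pearson test, exact enumeration. Each cell shows power in all subjects vs baseline positives only.

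| Clearance in baseline positives (placebo vs active) | q = 5% | q = 10% | q = 20% | q = 30% |
|---|---|---|---|---|
| 30% vs 45% | 63.0 vs 66.1 | 56.9 vs 63.6 | 46.3 vs 58.7 | 38.6 vs 52.4 |
| 50% vs 65% | 63.8 vs 65.6 | 59.8 vs 63.1 | 52.0 vs 58.3 | 44.1 vs 52.3 |
| 60% vs 75% | 69.2 vs 70.4 | 65.7 vs 68.6 | 58.4 vs 63.2 | 50.9 vs 57.6 |
| 70% vs 85% | 80.3 vs 81.2 | 77.2 vs 79.1 | 70.3 vs 74.2 | 62.4 vs 68.2 |
| Range of gap (points) | about 1–3 | about 2–7 | about 4–12 | about 6–14 |

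The baseline-positive analysis has more power in every cell, despite fewer subjects. The gap is largest when clearance is low.

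**The case against.** **ITT is a valid analysis.** It compares all randomized subjects as assigned and controls type I error. Restricting to baseline positives answers the question for a different population. This stands. A reader might infer that the ITT result is biased; the accurate description is that it is diluted relative to the effect in subjects who were shedding at baseline. Both documents use ITT for the secondary endpoints, and the protocol makes the confirmed-case set a sensitivity analysis, so they do not require that the two be swapped.

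**A baseline negative is not a guaranteed success.** Protocol 8.3 explains retention by the imperfect sensitivity of RT-PCR, so a subject negative at baseline may test positive later and count as shedding. This stands, and is why s is set at 95% rather than 100%.

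**The SAP does not cancel the analysis.** It refers readers to the protocol for further detail, and its table list is marked draft. A reader might infer a deliberate withdrawal, but the documents show only silence. Given the precedence and stand-alone wording, silence still leaves the analysis without a definition, method or table.

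**The protocol's motive.** It is tempting to say that the protocol planned the confirmed-case analysis to deal with this dilution. Protocol 13.3 gives no reason, so that cannot be claimed.

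**The loss may be small.** At q = 5% the power gap is only about 1 to 3 points, and viral shedding has no power target. This is fair: the size is unknown until q is known.

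**Conclusion.** The point holds as an omission with a quantifiable consequence. The protocol's confirmed-case sensitivity analyses, for the primary and secondary efficacy endpoints, and its viral-shedding shift table are missing from the governing SAP. For viral shedding, retained central-negative subjects shrink the ITT difference by the factor (1 − q) if they behave alike in both arms. With the assumed 15-point difference, placebo clearance of 30% to 70% and q of 5% to 30%, power in all subjects falls about 1 to 14 points short of that in baseline positives alone. These inputs are illustrative, because the documents supply neither clearance rates nor q. The formula does not depend on the particular values chosen. The omission on its own warrants correction, whatever q proves to be.

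**What to change.** Before unblinding:

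1. In SAP 2.5, define a central-laboratory-confirmed set: randomized subjects with a positive central RT-PCR on the pre-dose baseline swab. Tie it explicitly to that swab, so that membership cannot depend on anything after treatment starts, and state how a missing baseline result is handled.
2. In SAP 4.1 and 4.2, restore the sensitivity analysis in this set for the primary endpoint and for the secondary efficacy endpoints, including viral shedding at Day 7 and Day 15.
3. Add the matching tables and a viral-shedding shift table from baseline by arm. The shift table would also show q directly.

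ITT may stay the main analysis throughout. Making baseline positives the main set for viral shedding, with ITT as support, is optional.

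The cost is SAP wording and a few more tables. The swab is already collected, so no new data are needed. The downside is a smaller denominator in the confirmed set.

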5.1 Background on COVID-19

5.1.1 Overview of COVID-19 Disease

[Gandhi et al, 2020](#) discusses the presentation, management, prevention, and control of patients with mild or moderate COVID-19. SARS-CoV-2 is a novel betacoronavirus related to bat coronaviruses that was thought to originate from a seafood market in Wuhan, China, where live animals were sold. There is much still unknown about COVID-19, but data from China indicated that 81% of people who become infected have a mild or moderate form of the disease (with no or mild pneumonia), 14% have a severe disease, and 5% have a critical form of the disease.

COVID-19 is spread from person to person through an infected person's respiratory droplets from coughs, sneezes, or even just speaking. It may also be contracted from a contaminated surface when a person touches the surface and then touches their face, transferring the virus to a mucosal membrane. Droplets are able to travel for approximately 2 meters from the infected person and then fall. Standing at least 1.8 meters (6 feet) apart from others will reduce the likelihood of transmission. The virus may live on certain surfaces (cardboard, plastic, and stainless steel) for days; therefore, sterilizing surfaces with antibacterial cleaners will also reduce transmission. Personal protective equipment for health care workers is essential to prevent the spread of COVID-19. Testing and diagnosis of patients is important so that those who are infected can self-isolate to prevent the spread to others ([Gandhi et al, 2020](#)).

An infected person may or may not display symptoms. Presymptomatic people may infect others for 1 to 3 days before displaying symptoms, and the virus is detectable during this time. The time from exposure to the time of displaying symptoms can be from 2 to 14 days, with 97.5% of people displaying symptoms within 11.5 days after infection. Patients usually have high viral levels in nasopharyngeal samples just before or soon after symptoms start. Viral levels will

continue to be detectable but will fall over the next week. Patients with severe COVID-19 illness may continue viral shedding longer, but how long viral shedding continues is not known at this time ([Gandhi et al, 2020](#)).

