10.1 Study Visits

10.1.1 Screening/Baseline and Day 1 Visit

The following procedures and assessments will be done at the onsite Screening/Baseline and Day 1 visit:

- Verify subject has written notification from a local laboratory confirming COVID-19 infection within 72 hours of randomization (i.e., Day 1). In most instances, the Screening/Baseline visit will occur on the same date as Day 1. If needed, the Screening/Baseline may occur before Day 1 as long as randomization can be completed within the 72-hour window.
- Obtain informed consent
- Review of inclusion/exclusion criteria, including urine pregnancy test, if applicable
- Assign a subject ID number (ID number = XXX site number followed by 001, 002, 003 subject number)
- Obtain mid-turbinate nasal swab sample to be sent to the central laboratory to test for a baseline assessment and to test for viral shedding of COVID-19 by RT-PCR
- Draw blood for central laboratory testing
- Record demographics, medical history (including current COVID-19 symptoms), and concomitant medications
- Obtain vital signs (height, weight, heart rate, blood pressure, SpO2)
- Measure oral body temperature
- Perform randomization and dispensing of study drug
- Provide subject with instructions for accessing eDiary portal for collection of daily information
- Administer first dose of study drug after all assessments are completed
- Record of any TEAEs

10.1.2 Onsite Visits on Day 7, Day 15, Unscheduled Visit, Early Termination Visits / Telephone Visits on Day 21, Day 28

The following procedures and assessments will be done on Day 7, Day 15, Day 21, Day 28, and early termination by telephone or at onsite visits:

- Verify subject compliance for completing daily eDiary entries by accessing the web portal for the subject's eDiary
- Review concomitant medications and record any TEAEs
- Assess vital signs (heart rate, blood pressure, SpO2) during on-site visits only
- Measure oral body temperature
- Draw blood for central laboratory testing (Day 15, Unscheduled Visit and Early Termination) during on-site visits only

- Obtain mid-turbinate nasal swab sample for viral shedding test (Day 7, Day 15, and Early Termination Visits) for central laboratory during on-site visits only

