4.1.7 Handling of Missing Data for the Primary Efficacy Test

To provide a true ITT efficacy test, subjects lost-to-follow-up prior to Day 28 must be imputed. A multiple imputation (MI) (Rubin and Schenker 1991)³ strategy will be used in the primary efficacy test followed by a completers analysis and a tipping point analysis as sensitivity analyses that examine the robustness of the Missing at Random (MAR) assumption necessary for valid application of MI.

To implement the MI for primary efficacy testing, 20 imputed data sets will be constructed. If the pattern of missing data is not monotonic, a fully conditional (FCS) approach as implemented in SAS PROC MI (SAS Institute)⁴ will be utilized. If the pattern of missing data is monotonic, a regression approach may be used. The MI model will include age, BMI, sex, and the number of days since first COVID-19 symptom (≤ 5 or > 5 days), as well as temperature at Day 7 and 14 taken at the clinic. Should the pattern of missing data be non-monotonic, an FCS model will be utilized. The estimated treatment group difference and standard error will be determined for each imputed data set and combined using Rubin's rule as implemented in SAS PROC MIANALZE. The final treatment group difference will be the average of the multiple imputed datasets. The standard error, p-value, and width of the confidence interval will account for both within and between imputation error.

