The validity of the MI depends on the assumption of Missing at Random (MAR). MAR means that the likelihood of missingness does not depend on the unobserved event status. A tipping point analysis will be performed to evaluate the robustness of this assumption. First a completer's analysis will be performed in which only subjects with complete endpoint status (that is, did not withdraw early or discontinue) are included. Then, all subjects with missing data are included in the analysis varying the numbers of subjects assumed to have experienced the event in both groups separately. This analysis includes the worst-case scenario in which all missing treated subjects are assumed to have experienced the event and all placebo subjects are assumed to have not experienced the event. It also includes the best-case scenario, in which all missing treated subjects are assumed to have not experienced the event and all placebo subjects are assumed to have experienced the event. All other scenarios are similarly evaluated. Assuming superiority has been demonstrated, the percentage of scenarios in which the results change from rejecting the null hypothesis to not rejecting the null hypothesis is determined.

If this percentage of scenarios in which study conclusions change is small (for example, less than 20%), then the superiority conclusion has been shown to be robust with regard to missing data.

As requested by FDA, an additional sensitivity will be provided in which all missing data are treated as failures.

If an exact test is necessary for the primary endpoint due to expected cell counts < 5 in either group, only the tipping point analysis based on the exact tests will be provided.

³ Rubin DB and Schenker N. Multiple imputation in health-care databases: an overview and some applications. *Statistics in Medicine* 10: 585-598, 1991.

⁴ Version 9.4, SAS Institute Inc, Cary, NC

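### Viral shedding takes over the primary endpoint's imputation by cross-reference, with no rule for swabs missing because the subject had died or was in hospital

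*SAP*

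**What the plan says.** SAP 4.2.2 gives viral shedding at Day 7, Day 15 and early termination no analysis of its own. It states that the proportion "will be analyzed using the approach specified for the primary endpoint".

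The missing-data part of that approach is SAP 4.1.7. It begins: "To provide a true ITT efficacy test, subjects lost-to-follow-up prior to Day 28 must be imputed". It then specifies that "20 imputed data sets will be constructed". On the predictors it says: "The MI model will include age, BMI, sex, and the number of days since first COVID-19 symptom", "as well as temperature at Day 7 and 14 taken at the clinic". Its assumption is put as follows: "MAR means that the likelihood of missingness does not depend on the unobserved event status". The sensitivity analyses are a completers analysis, a tipping-point analysis that includes best and worst cases, and one that counts every missing value as a failure. If expected counts fall below 5, imputation is dropped and only the tipping-point analysis on exact tests remains.

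Protocol 10.1.2 lists the swab thus: "Obtain mid-turbinate nasal swab sample for viral shedding test (Day 7, Day 15, and Early Termination Visits) for central laboratory during on-site visits only". Protocol 8.5 exempts death and hospitalization from the effort to follow discontinued subjects to Day 28. Protocol 5.1.1 remarks: "Patients with severe COVID-19 illness may continue viral shedding longer".

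Fever resolution is treated differently. SAP 4.2.2 counts a subject who dies before resolution as unresolved at Day 28, and SAP 4.1.8 gives fever its own missing-data rule. Viral shedding has neither. Protocol 13 leaves missing data to the SAP.

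**The concern.** The imputation was designed for an endpoint in which hospitalization, emergency-room visit and death are the outcome itself (SAP 3.1). Leaving them out of the predictors does no harm there, because a subject with such an event is not missing.

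For shedding the same events become a cause of missing data. A subject who has died cannot give a swab, and one in hospital is unlikely to attend the clinic for it. The listed predictors contain no trace of the event and no earlier RT-PCR result. The only post-baseline predictor, clinic temperature, comes from clinic visits and will usually be missing along with the swab. The missing result is then filled in mainly from four baseline variables, as though the subject resembled those who attended. The imputed value can be a success.

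This is the trial's only virological endpoint, for a drug whose rationale is blocking viral entry (Protocol 7.2). SAP 4.1.6 rests the Phase III decision on the totality of the evidence.

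**Working it through.** **1. The role of the event in the two endpoints**

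| | Primary endpoint | Viral shedding |
|---|---|---|
| Hospitalization, ER visit or death | Observed failure (SAP 3.1) | Possible cause of a missing swab |
| Event status in the listed model | Not needed | Not listed |
| Earlier central RT-PCR (baseline, Day 7) | Not needed | Not listed |
| Treatment | Not listed | Not listed |
| Rule for death | Counts as event | None (fever has one) |

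**2. The plan's own figures**

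Neither document gives a figure for shedding. The event rates used below, 15% on camostat and 30% on placebo, come from Protocol 13.1. Exact enumeration of two-sided Fisher power at 183 and 92 subjects gives 80.2% against the stated 80%, so the protocol's calculation reproduces. At the planned 200 and 100, expected events are 200 × 0.15 = 30 and 100 × 0.30 = 30.

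**3. Illustration of the imputation**

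Assumptions not in the documents: clearance is 70% in event-free and 40% in event subjects, in both arms, and a share f of event subjects has no swab.

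True clearance:
- Camostat: 0.85 × 0.70 + 0.15 × 0.40 = 65.5%
- Placebo: 0.70 × 0.70 + 0.30 × 0.40 = 61.0%
- Difference: +4.5 points

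An imputation without event status or treatment gives each missing swab the pooled observed rate

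r = [240 × 0.70 + 60(1 − f) × 0.40] / [240 + 60(1 − f)]

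where 240 = 170 + 70 event-free subjects and 60 = 30 + 30 event subjects. The part of the true difference that is lost is f × (r − 0.40) × (0.30 − 0.15).

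- f = 1: r = 168/240 = 0.700. Lost 1 × 0.300 × 0.15 = 4.5 points, leaving 0.
- f = 0.5: r = 180/270 = 0.667. Lost 0.5 × 0.267 × 0.15 = 2.0 points, leaving +2.5.
- f = 0.25: r = 186/285 = 0.653. Lost 0.25 × 0.253 × 0.15 = 0.9 points, leaving about +3.6.

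Within these clearance rates f = 1 is the upper bound. If event subjects cleared at the same rate as the others, nothing would be lost. If events were commoner on camostat, the sign would reverse and the imputation would hide harm.

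**4. The obvious remedy under the same assumptions**

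Score every event subject without a swab as not cleared.
- f = 1: 0.85 × 0.70 = 59.5% against 0.70 × 0.70 = 49.0%, a difference of +10.5 points. This overshoots the assumed truth by 10.5 − 4.5 = 6.0 points, more than the 4.5 that the imputation loses.
- In general the overshoot is f × 0.40 × 0.15: 3.0 points at f = 0.5 and 1.5 points at f = 0.25.

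**5. How far the scoring rule moves the result**

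Suppose swabbed subjects clear at a common rate q in both arms. Imputation then gives a difference of about 0, and scoring as not cleared gives q × f × 0.15. From q = 0.5, f = 0.25 to q = 0.9, f = 1 this runs from 1.9 to 13.5 points. The range is the distance between two scoring rules and does not measure bias.

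**The case against.** **Imputation reaches shedding only by cross-reference.** SAP 4.1.7 is titled for the primary efficacy test and speaks of subjects lost to follow-up. A subject known to be in hospital or dead is not lost in that sense, and fever has its own section. The approach could mean only the chi-squared or Fisher test of SAP 4.1.1. This stands as a doubt. Reading 4.1 as a whole is the more natural course, and on the narrow reading these subjects are dropped or unclassified, so a rule is still missing.

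**The sensitivity analyses would carry over too.** Completers, worst case, tipping point and all-missing-as-failure would expose the problem. This also stands, but they would sit beside a main result that has no rule for these subjects, and the SAP does not say that they will be reported for shedding. Likewise, imputing Day 7 and Day 15 jointly or by arm would bring in the earlier result or treatment, but the SAP does not say so.

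**The 28-day event rates overstate missing swabs.** An event after the swab day removes nothing. A subject with only an emergency-room visit may still attend, a discharged subject may return, and an Early Termination swab may exist. This stands in full and is why f = 1 is only an upper bound.

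**Missing at random is not shown to fail.** The Protocol 5.1.1 remark on longer shedding in severe illness is hedged, and the sentence goes on to say that the duration is unknown. It supports doubt about the assumption and no more.

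**Conclusion.** The gap is real and should be closed. As the SAP most naturally reads, a subject with no swab because of death or hospitalization can be imputed as cleared, from a model that lists neither the event nor earlier RT-PCR results, while the same section has a death rule for fever.

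A reader might infer more than the documents support:
- That the SAP expressly imputes these subjects. It does so only through the cross-reference.
- That a real benefit of 4.5 points will be lost. That figure rests on assumed clearance of 70% and 40% and on every event subject lacking a swab. The documents give neither clearance nor the share without a swab, so size and direction cannot be computed.
- That all hospitalized subjects without a swab should count as not cleared in the main analysis. In the illustration this overshoots, because it brings the clinical endpoint into the virological one.

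Shedding is a secondary endpoint and no success rule hangs on it, so the point does not touch the primary conclusion.

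**What to change.** In SAP 4.2.2, give viral shedding its own missing-swab rule, fixed before unblinding:

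1. Count a subject who died before the swab day as not cleared, in line with the fever rule.
2. Impute other missing swabs from the listed predictors plus treatment, the baseline central RT-PCR result, the Day 7 result (for Day 15), and primary-event status on or before the swab day.
3. Report two sensitivity analyses: observed swabs only, and the composite that scores hospitalized subjects without a swab as not cleared. If discharge dates are not available, define the composite as an event on or before the swab day with no swab.
4. Report by arm and day how many event subjects lack a swab. If few or none have one, the effect of event status cannot be estimated in the model, and the sensitivity analyses must carry that uncertainty.

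The cost is SAP wording, one derivation rule and a longer predictor list. The swab results and event status are already collected, and the time-to-event endpoint already needs event dates. The death rule does add a clinical component to the endpoint; the observed-only analysis shows the result without it.
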